10.8 Secondary endpoint analysis

A Poisson regression analysis with a random effect for individuals to allow for over-dispersion will be applied to determine the influence of allocation on number of days with parent-reported wheeze, number of admissions to hospital, number of admissions to hospital > 4 hrs duration. An incident rate ratio for each factor will be presented with 95% confidence intervals.

Time to first attack of wheeze will be analysed using a log-rank test with adjustment for clustering and, if hazards are proportional, Cox's proportional hazards models adjusting for clustering. In a Cox model, strata and centre will be included as covariates.

Other continuous variables will be analysed with analysis of covariance. Dichotomous variables will be analysed with logistic regression analysis.

Adverse events will be analysed with descriptive statistics.

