5.5 Method for assigning subjects to treatment group

Randomisation will be stratified according to ALOX5 promoter polymorphism status. This will yield two genotype groups:

[figure not shown]
Group I Children with the [5/5] ALOX5 promoter polymorphism genotype. **Group II** Children with [5/x and x/x]" ALOX5 promoter polymorphism genotype; where x is > or < than 5 SP1 repeats. (Groups will be referred to as Stratum A or B – all trial staff will be blinded to this relationship except the laboratory technician).

For children (participants) in each of these two genotype groups (strata) we will assign consecutive randomisation numbers from randomised permuted blocks of 10. Within each block equal numbers of children will be randomly allocated to placebo and active treatment. When all numbers from the first block have been assigned a new block of randomisation numbers will be allocated to that stratum, until a total of 1300 children in the two strata combined have been assigned a randomisation number. If a randomisation number is assigned to a child who does not subsequently take any dose of IMP, the IMP bearing that randomisation number will be returned to pharmacy, and the randomisation number may be assigned to another child (participant) provided that that medication has not been dispensed.

[figure not shown]
WAIT Trial_ Protocol_v7_24th June 2011

[figure not shown]
Page 24 of 58

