10.1.2 Secondary Endpoints

The secondary outcome measures for this trial are:

Respiratory morbidity

- Number of admissions to hospital over the 12 month trial period
- Duration of admissions to hospital over the 12 month trial period
- Time to first attack of wheeze
- Number of unscheduled GP consultations for wheeze
- Duration of episodes by diary card
- Severity of episodes by diary card
- · Parents' overall impression of efficacy of IMP

Health service use

- Unscheduled GP consultation with exacerbation of wheeze, expressed as time from randomisation to first attendance and annual attendance rate
- A&E attendance with wheeze exacerbation, expressed as time from randomisation to first attendance and annual attendance rate
- Unscheduled hospital admission with wheeze exacerbation, expressed as time from randomisation to first admission and annual rate of admissions
- Total duration of hospital admissions for exacerbation of wheeze

Adverse events

- Severe adverse events
- Withdrawal from the trial
- Mortality due to exacerbation of asthma
- Mortality due to respiratory infection
- All-cause mortality

Medication use

- Use of oral corticosteroids, expressed as number of courses taken per year, and proportion of children receiving at least one course of oral corticosteroids during the trial
- Use of inhaled relief medication (salbutamol), expressed as mean usage per wheeze episode as recorded in diary card by parent guardian.
- Use of inhaled corticosteroids (ICS), expressed as mean daily dose of beclometasone equivalent over the 12 month trial period.
- Regular prescription of inhaled ICS over the 12 month trial period

Inflammatory outcomes

Association between baseline urinary cysteinyl leukotriene level and:

WAIT Trial_ Protocol_v7_24th June 2011

Page 41 of 58

- ALOX5 status
- Other polymorphisms of leukotriene genes
- Previous history of viral-triggered episodic and multi-trigger
- Responsiveness to montelukast
- Acute history of wheeze

Genetic parameters

- Differential responsiveness to montelukast for the primary outcome in the stratum with ALOX5 promoter polymorphism [5/5], compared with the stratum with the ALOX5 [5/x + x/x] genotype.
- Differential responsiveness to montelukast for the primary outcome resulting from other polymorphisms in genes influencing leukotriene synthesis, leukotriene metabolism and leukotriene activity.

Economic outcomes

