10.2 Statistical considerations

10.2.1 Sample Size

This trial is powered to detect a clinically significant difference in the number of attacks of wheeze between intervention and control arms. We also have some power to detect differential responsiveness (in terms of the primary outcome) to montelukast in the stratum with ALOX5 promoter polymorphism [5/5], compared with the stratum with the ALOX5 [5/x and x/x]" genotype.

Baseline data on mean (0.76) and standard deviation (1.22) of number of attacks are based on data from the UK General Practitioner Research Database on courses of oral steroids (a proxy for number of episodes). These data follow an overdispersed Poisson distribution. To take account of this we used markov chain Monte Carlo simulation in WinBUGs to estimate sample sizes required: (WinBUGS Version 1.4. 2003 Available from: http://www.mrc-bsu.cam.ac.uk/bugs/welcome.shtml). To detect a 33% drop in attack rate requiring medical attention, with a power of 90% and at a significance level of 5%, and a 6% loss to follow up, we require 1050 children in total. A 33% drop in attack rates equates to an attack rate of 0.51 for the treatment group. The clinical significance of these changes is that approximately four children will need to be treated to prevent one clinically severe attack. A sample size of 1200 gives just over 80% power at the 5% significance level to detect an interaction between treatment and genotype if the effect is a 60% reduction in the [5/x plus x/x] and a 20% reduction in the [5/5] stratum. Assuming a 6% dropout, 1300 children will need to be recruited.

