10.7 Analysis of primary endpoints

Initial analyses will be performed according to intention-to-treat for all participants with outcome data. Per protocol efficacy analyses will also be performed, excluding data collected after discontinuation of IMP for those participants who discontinue IMP. We will use Poisson regression with a random effect representing individuals to account for overdispersion. Fixed effects will represent the stratification factor (ALOX5 promoter) and treatment centre. The incident rate ratio (relative risk) and 95% confidence interval will be calculated. Analysis will be conducted in Stata version 10. To test for a differential effect by stratum an interaction between stratum and treatment will be fitted to this model as described in 10.8.1.

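### Section 10.8 prescribes a clustering adjustment for time to first wheeze, but children are individually randomised and the protocol never says what the clusters are

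*Protocol*

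**What the plan says.** Section 10.1.2 lists "Time to first attack of wheeze" among the secondary outcomes. Section 10.8 begins its analysis with "Time to first attack of wheeze will be analysed using a log-rank test with adjustment for clustering", and the sentence as a whole applies the adjustment to both methods: "a log-rank test with adjustment for clustering and, if hazards are proportional, Cox's proportional hazards models adjusting for clustering". It then adds: "In a Cox model, strata and centre will be included as covariates". That last sentence is confined to the Cox model; for the log-rank test neither factor is mentioned.

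The design is set out in Section 5.5: "Randomisation will be stratified according to ALOX5 promoter polymorphism status", using permuted blocks of ten, and "Within each block equal numbers of children will be randomly allocated to placebo and active treatment". Centre is not a randomisation stratum. For the primary count outcome, Section 10.7 states: "Fixed effects will represent the stratification factor (ALOX5 promoter) and treatment centre". The random effect in that model represents the individual child and is there for overdispersed counts.

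**The concern.** A clustering adjustment is needed when groups are randomised, or when one subject contributes several correlated outcomes. Neither applies here: allocation is by child, and a first-event endpoint gives at most one event per child. The individual random effect used for counts has no counterpart in a first-event analysis.

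The protocol does not leave the matter open. It fixes an adjustment without saying what it is for. An analyst must then choose a cluster (centre, practice or family) and a method (sandwich variance, frailty or stratification), and these choices can give different p-values. The obvious grouping is centre, for which a cluster-robust variance is a common choice, and that variance is unreliable when there are few clusters or a few dominate. At stake are the p-value and confidence interval of one listed secondary outcome.

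Separately, the log-rank test is written without the factor used to stratify randomisation, although the Cox model includes it.

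**Working it through.** **1. Does the protocol contain a cluster?**

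| Candidate | What the protocol shows |
|---|---|
| Randomised group | None; children are allocated individually (Section 5.5) |
| Repeated events in a child | None; only the first event counts (Section 10.1.2) |
| Centre | Covariate in the Cox model (10.8), fixed effect in the primary model (10.7) |
| GP practice | A recruitment route (5.2.1), not named as a cluster |
| Siblings | Neither excluded (4.2) nor mentioned |

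The sample size also makes no visible allowance for clustering. Section 10.2.1 gives: "Baseline data on mean (0.76) and standard deviation (1.22) of number of attacks", a treated rate of 0.51, 90% power, 5% significance (two-sided assumed) and 6% loss. The simple two-means formula gives

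n per arm = 2 × (1.960 + 1.282)² × 1.22² / (0.76 − 0.51)² ≈ 501,

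so 1002 in total, and 1002 / 0.94 = 1066 after loss. This is within 2% of the stated 1050 with no design effect.

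**2. What happens if centre is taken as the cluster?**

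The direction of the error depends on the form of the test. Let G be the number of centres.

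*Wald test with sandwich variance.* With equal centres, the estimate over its robust standard error behaves roughly like a t variable on G − 1 degrees of freedom. Comparing it with 1.96 gives a type I error of 2·P(t > 1.96):

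- G = 3: 0.189
- G = 10: 0.082
- G = 40: 0.057

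*Cluster-robust log-rank score test.* With centre scores U_g, Z = ΣU_g / √{[G/(G − 1)]·ΣU_g²}. Since |ΣU_g| ≤ √(G·ΣU_g²), |Z| cannot exceed √(G − 1). For G = 3 the ceiling is √2 = 1.41, so the test can never reach 1.96.

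*Simulation.* Null trials of 1300 individually randomised children in blocks of ten within two strata, first-event rate 0.76 per year, 12-month censoring, G/(G − 1) factor and normal reference. The Wald runs used a model with treatment only and 3000 trials per layout. The score-test runs used 4000 trials and included between-centre frailty. Centre sizes are assumptions. Where separate runs differed, the range is shown.

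| Centres | Wald, clustered | Score log-rank, clustered | Ordinary test |
|---|---|---|---|
| 3 | 18–22% | 0% | 4.7–5.1% |
| 3 large + 20 small | 10–11% | 2.6–3.5% | 5.1% |
| 10 equal | 8.1% | not run | 4.9% |
| 40 equal (score test: 40–60 centres) | 5.9% | 4.4–5.1% | 5.3% |

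The Monte Carlo standard error at 5% with 3000 trials is √(0.05 × 0.95 / 3000) = 0.4 points.

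Real differences between centres do not rescue the adjustment. With a between-centre log-hazard SD of 0.3 (assumed), the Wald test gave 8.0% clustered against 5.2% ordinary with ten centres, and 6.5% against 6.2% with forty. Treatment varies within centre, so the ordinary test needs little protection.

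**3. What does leaving ALOX5 out of the log-rank cost?**

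Simulation with 1220 children analysed and gamma frailty matched to mean 0.76 and SD 1.22. Assumptions: 40% of children in the variant stratum, with a baseline rate 1, 1.5 or 2 times that of the 5/5 stratum. Each cell shows unstratified / stratified.

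| Rate ratio of strata | Type I error | Power, 33% reduction | Power, 25% reduction |
|---|---|---|---|
| 1 | 0.045 / 0.044 | 0.912 / 0.912 | 0.660 / 0.659 |
| 1.5 | 0.043 / 0.045 | 0.921 / 0.922 | 0.685 / 0.690 |
| 2 | 0.048 / 0.053 | 0.907 / 0.908 | 0.660 / 0.671 |

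The largest gain is 0.671 − 0.660 = 0.011, about one percentage point of power. Validity is not in question.

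**The case against.** The strongest reply is that the error rates belong to one implementation. Section 10.8 states neither centre as the cluster, nor a sandwich variance, nor a normal reference. Other readings behave well: a log-rank test stratified by centre gave 4.4–5.8% in every layout, three centres included, and a robust variance clustered on sibling pairs (10% of children, assumed) gave 5.1%. This stands. The inflation is a possible result of the text, not a necessary one, and for the log-rank itself the distortion can be conservative. It does not remove the point, because the protocol does not say which of these is meant.

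Second, three centres is an extreme case. The Study Summary names three but allows more, and the contents list shows Appendix A with secondary care sites from page 48 and primary care sites from pages 55 and 57. The number and sizes of these sites cannot be seen here. With many similar-sized centres the problem nearly vanishes. With many unequal ones it need not: 23 centres of which three dominate still gave about 10% for the Wald test.

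Third, siblings may be enrolled and practices are a recruitment route, so some correlation may exist. That is a reason to name the cluster, not to leave it undefined.

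Fourth, stratification of the log-rank is a detail that an analysis plan could supply. That also stands, and this part is only a consistency point.

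**Conclusion.** The point holds as a minor one. Section 10.8 fixes a clustering adjustment for a first-event analysis of individually randomised children, defines no cluster, and already handles centre by covariate adjustment.

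The size is conditional. It assumes centre as cluster, a cluster-robust variance, a normal reference and the centre layouts shown; the Wald runs also left out the planned covariates. On that footing the error rate is wrong in one direction for a Wald/Cox test and in the other for a score log-rank when centres are few or unequal, and close to nominal with about forty.

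A reader might infer three stronger things that the protocol does not support:

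- That the planned test has a type I error near 20%. This needs three centres and an implementation that the text does not state.
- That the log-rank test is invalid without the ALOX5 strata. It remains valid, and about one point of power is involved.
- That no correlation between children is possible. Siblings are not excluded.

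One secondary outcome is affected. The primary Poisson analysis and the sample size do not depend on it.

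**What to change.** In Section 10.8, delete both clustering phrases. Specify a log-rank test stratified by ALOX5 group, which brings it into line with the randomisation and the Cox model, and a Cox model adjusted for ALOX5 group and centre with model-based standard errors.

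If a real cluster was intended, such as siblings, keep an adjustment but name the unit and the method before unblinding.

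The cost is a change of wording. No extra data, children or analysis effort are needed.

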10.8.1 Genetic Analysis

To assess the difference in responsiveness to montelukast in the two ALOX5 strata we will fit an interaction term to test for the interaction between montelukast and stratum in our main model, or each treatment limb. We will also report the associations between genotype and clinical phenotype, urinary leukotriene level, and clinical outcome. To test the polymorphisms in each gene in combination, we will use a composite likelihood approach which combines the regression coefficients for all polymorphisms at each locus. Analysis of clinical effectiveness (utility) of stratification of ALOX5 status will utilise *in vitro* diagnostic multivariate index assays (IVDMIA's). We will estimate the benefits of a multivariate index assay based on our data in both clinical and economic terms (e.g. days off school days off work for parents' costs of attendance at GP and hospital, costs of treatment).

10.8.2 Pre-specified sub-group analyses

There are 2 pre-specified subgroups for analysis (other than ALOX5 genotype detailed above):

- Parent-reported history of multi-trigger vs viral episodic wheeze phenotype prior to enrolment
- Basal urinary leukotriene concentration

10.8.3 Health economic analysis

Determination of costs

Costs will be obtained by recording units of resources used, and applying tariffs to each. Important units are visits to primary care, use of out-of-hours services and A&E, prescriptions, over-the-counter drugs, hospitalisations and bed-days. Resource use will be costed using the appropriate national tariff for each type of unit cost; when unavailable, we will use the costs charged for tests carried out in the study. Unit costs for general practitioner and nurse consultations, other primary care services and outpatient attendances will be obtained from the Unit Costs of Health and Social Care 2005. These unit costs are inclusive of ancillary staff costs, overheads and training costs. Unit costs for elective and acute hospital admissions will be obtained from the Reference Costs Database. Unit drug costs per daily dose will be calculated from the Prescription Cost Analysis Database. Unit costs for diagnostic tests will be obtained from published primary costing studies conducted in the UK. Parental costs will be obtained from the telephone interview and will include time off work due to their child's wheeze and time taken to seek medical advice as well as travel expenses and out-of-pocket expenses on additional drugs. The costs associated with non-prescription drugs and visits for private health care will also be recorded. Parental time lost from work and time taken to seek medical advice due to exacerbations will be valued using age- and sex-adjusted average daily wage rates from the Office for National Statistics New Earnings Survey, 2003

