Study Centres	Barts and The London NHS Trust; University of Leicester NHS Trust, Grampian NHS Trust (others may be added as required – see appendix)					
Primary objective (phase of trial)	To determine whether parent-initiated intermittent treatment with oral montelukast in preschool children reduces the need for unscheduled medical attention for upper or lower respiratory tract infection or wheeze (Phase 3 trial).					
Number of Subjects/Patients	1300					
Main Inclusion Criteria	 Medical record diagnosis of wheeze, two previous attacks of wheeze one being within the last 3 months. Age ≥ 10 months and ≤ 5.0 years at recruitment 					
Statistical Methodology and Analysis	The incident rate ratio (relative risk) and 95% confidence interval for need to seek unscheduled medical attention.					

Glossary of Terms and Abbreviations

AE Adverse Event

ACT Asthma Control Test
AR Adverse Reaction

ALOX5 membrane bound 5-lipoxygenase

ASR Annual Safety Report
CA Competent Authority

Child An individual who takes part in this clinical trial

CI Chief Investigator

CRF Case Report Form

CRO Contract Research Organisation

CTA Clinical Trial Authorisation

CTIMP Clinical Trial of Investigational Medicinal Product

DMC Data Monitoring Committee

EC European Commission

EMEA European Medicines Agency

EU European Union

EUCTD European Clinical Trials Directive
EudraCT European Clinical Trials Database

EudraVIGILANCE European database for Pharmacovigilance

GAFREC Governance Arrangements for NHS Research Ethics

GCP Good Clinical Practice

GMP Good Manufacturing Practice

IB Investigator Brochure
ICF Informed Consent Form

IMP Investigational Medicinal Product

IMPD Investigational Medicinal Product Dossier

ISRCTN International Standard Randomised

IVDMIA In vitro diagnostic multivariate index assay

JRO Joint Research and Development Office

MA Marketing Authorisation

MHRA Medicines and Healthcare products Regulatory Agency

WAIT Trial_ Protocol_v7_24th June 2011 Page 15 of 58

Protocol as approved by National Research Ethics Service Reference 09/H1102/110 Date 23rd November 2009 MS Member State

Main REC Main Research Ethics Committee

NHS R&D National Health Service Research & Development

PAG Parental Advisory Group

PI Principle Investigator

QA Quality Assurance

QC Quality Control

QP Qualified Person for release of trial drug

RCT Randomised Control Trial

REC Research Ethics Committee

SAR Serious Adverse Reaction

SAE Serious Adverse Event

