10.2.2 Planned recruitment rate

We plan to recruit 1300 children (participants) over 2 years.

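### The costing rule fixes 2005 unit costs and 2003 wages beside trial-time amounts, with no common price year, so cost totals would mix price years

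*Protocol*

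**What the plan says.** Section 10.8.3 (Health economic analysis) sets the price sources item by item.

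- **GP, nurse, other primary care and outpatient contacts:** a fixed edition, "outpatient attendances will be obtained from the Unit Costs of Health and Social Care 2005".
- **Parental time lost from work or spent seeking advice:** a fixed survey, "average daily wage rates from the Office for National Statistics New Earnings Survey, 2003".
- **Admissions:** "Unit costs for elective and acute hospital admissions will be obtained from the Reference Costs Database", with no year.
- **Drugs:** "Unit drug costs per daily dose will be calculated from the Prescription Cost Analysis Database", with no year.
- **Diagnostic tests:** "Unit costs for diagnostic tests will be obtained from published primary costing studies conducted in the UK", with no year.
- **General rule:** "Resource use will be costed using the appropriate national tariff for each type of unit cost", with no year. Where no tariff exists, the fallback is what was charged for tests done in the study.
- **Parents' travel and out-of-pocket spending:** collected at the telephone interviews, so in prices of the time. Non-prescription drug and private-care costs are also recorded.

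The section states no common price year and no uprating.

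The page footer gives the ethics approval as "Reference 09/H1102/110 Date 23rd November 2009". The Study Summary dates version 7 to 24 June 2011 and gives a study duration of 3 years. Section 10.2.2 says "We plan to recruit 1300 children (participants) over 2 years", and each child is followed for 12 months.

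**The concern.** Money amounts can be added only when they are in the prices of one year. Here two sources are tied to years well before the trial and two years apart from each other, and they sit beside amounts that arise while the trial runs.

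Two planned results combine them. The parental cost outcome in section 10.1.2 puts travel and absence from work into one figure. Section 10.8.1 promises the benefit of an ALOX5-based index assay in economic terms, covering parents' time off work, GP and hospital attendance, and treatment. A total of this kind gives too little weight to any component held at old prices, if prices have risen since.

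The 2005 price also falls on a central resource item: GP attendance is one of the two settings that define unscheduled medical attention in section 10.1.3.

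**Working it through.** The protocol states no cost total, price year or inflation rate, so it has no figure to reproduce. The check has three parts: dates, mixing and size.

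**1. Age of the fixed sources (from the documents' dates)**

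| Reference date | Gap to 2005 unit costs | Gap to 2003 wages |
|---|---|---|
| Ethics approval, November 2009 | about 4 years | about 6 years |
| Protocol version 7, June 2011 | about 6 years | about 8 years |

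Approval is taken as the earliest plausible start of resource use, so the first row is a lower bound.

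**2. Mixing (no inflation figure needed)**

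Followed as written, parental cost = travel and out-of-pocket spending at trial-time prices + hours or days lost × 2003 wage. An NHS total adds GP and outpatient contacts at 2005 prices to items whose year is open, and possibly to test charges from the trial period. The two dated sources are already 2 years apart. The price basis therefore differs within a single outcome, however the undated sources are read.

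**3. Size (illustration under assumptions)**

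Assumptions, neither of them in the documents: annual growth g of 2–4% in prices and wages, and resource use centred on 2011 or 2012.

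Factor = (1 + g)^(year of use − price year). Shortfall in trial-time prices = 1 − 1/factor.

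| Item | Years | Factor at 2% | Shortfall at 2% | Factor at 4% | Shortfall at 4% |
|---|---|---|---|---|---|
| 2005 costs, use in 2011 | 6 | 1.126 | 11.2% | 1.265 | 21.0% |
| 2005 costs, use in 2012 | 7 | 1.149 | 12.9% | 1.316 | 24.0% |
| 2003 wages, use in 2011 | 8 | 1.172 | 14.7% | 1.369 | 26.9% |
| 2003 wages, use in 2012 | 9 | 1.195 | 16.3% | 1.423 | 29.7% |

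The ranges are about 11–24% for primary care and outpatient costs and about 15–30% for parental time. The gap between the two dated sources alone is 1.02² = 1.040 to 1.04² = 1.082, or 4–8%.

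Sensitivity: with growth of 1–5% and use in 2010–2013, the shortfalls are 5–32% and 7–39%. At zero growth there is none, and with falling prices the sign reverses.

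**4. Effect on a comparison of arms**

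Both arms take the same unit price. Within one cost category the ratio between arms and the sign of the difference do not change; the absolute difference is divided by the factor above. In a total across categories, the weights change: if parental time makes up a share s of parental cost in trial-time prices, that total is too low by s × 15% to s × 30%.

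**The case against.** The strongest reply is that a price year, uprating and the editions of undated databases are normally settled in an analysis plan, which is not at hand. That stands for the undated sources: their missing year is no fault in itself. It does not cover the two dated ones. The protocol names the editions, version 7 still carries them, and a plan that used current ones would depart from it.

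A second reply is that costing in the constant prices of an earlier year is legitimate. It is, provided that year is declared and common to all items. Here there are two such years, and expenses incurred during the trial sit beside them.

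A reader might go further and infer that the trial's costs as a whole are understated, or that savings from avoided GP visits and work loss are understated against drug and hospital costs. The documents support neither. They give no inflation or wage figure, and only primary care, outpatient and parental-time items are tied to old years. If hospital and drug prices were also taken for 2005, there would be no distortion between them and GP costs.

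Nor is June 2011 the start of the trial. It is the date of version 7, and resource use may already have been accruing by then. If the 3 years ran from approval, the mid-point would be about mid-2011.

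It is also fair to say that costs are a secondary outcome, that both arms are priced alike, and that section 10.8.3 sets no decision threshold that mispricing could cross. Days off work reported as counts are not affected.

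**Conclusion.** The point holds as a minor defect in a secondary analysis. Section 10.8.3 fixes 2005 unit costs and 2003 wages for resource use about 4 or more and 6 or more years later, and combines them with trial-time amounts without a common price year. The parental cost outcome and the economic estimate for the ALOX5-based assay would mix price years. This part rests on the documents alone.

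Direction and size rest on the assumptions of 2–4% annual growth and use centred on 2011–2012. Under these, primary care and outpatient costs are about 11–24% too low in trial-time prices, and parental time about 15–30% too low. No statement relative to hospital or drug costs can be made. The primary endpoint, sample size and power are untouched.

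**What to change.** In section 10.8.3, name one price year for all cost items. A year within follow-up is a natural choice, but any single declared year cures the mixing. Replace the 2005 unit-cost edition and the 2003 earnings survey with the editions for that year, or the nearest available. Uprate or deflate every other unit cost and recorded expense to it with a named index, and state the year for the admission, drug and test sources.

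This takes about two sentences. It needs no change to data collection, design or sample size, because resource use is recorded in units and priced afterwards.
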